4.3.2 Laboratory Parameters

Inflammatory markers included C-reactive protein (CRP), serum interleukin-6 (IL-6), serum tumor necrosis factor- α (TNF- α), and the systemic immune-inflammation index [SII, SII = (platelet count \times neutrophil count) / lymphocyte count].

Each parameter was assessed once preoperatively, on the day of surgery prior to treatment, and on postoperative Day 5.

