2.4.3.3 Abdominal acupuncture treatment

The initial abdominal acupuncture treatment was performed 4–6 hours after surgery, followed by one session daily from postoperative day 1 through day 4, yielding a total of five sessions per treatment course. Throughout the treatment period and thereafter, patients' clinical conditions were systematically recorded and evaluated, with concurrent monitoring of adverse events and concomitant medication use.

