2.4.4 Sample Size

This study was designed as a randomized controlled trial, with the treatment group receiving abdominal acupuncture and the control group receiving conventional therapy. The primary outcome measure was the time to first postoperative flatus. Based on published literature, the mean \pm standard deviation of the time to first flatus in the control group was 37.60 ± 4.11

hours. It was anticipated that abdominal acupuncture would reduce this time by approximately

8.1 hours. Assuming a two-sided $\alpha = 0.05$ and a statistical power of 90%, the sample size was

$$n = \frac{2(z_\alpha + z_\beta)^2 * \sigma^2}{\delta^2}$$

calculated using the standard formula:

The required sample size was determined to be 33 participants per group. With a 1:1 randomization ratio, both the abdominal acupuncture group and the control group required 33 participants each. Allowing for a potential 15% dropout or loss to follow-up, the minimum enrollment target was set at 38 participants per group, resulting in a total sample size of no fewer than 76 participants.

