4.3.3 Relevant Assessment Scales

- **Pain assessment:** The Visual analogue scale (VAS) was applied (Appendix 1). Abdominal pain scores were recorded before and after treatment on the day of surgery (5 days after surgery).
- **Gastrointestinal symptom assessment:** Symptom scoring was based on the Perioperative Clinical Evaluation Standards for Gastrointestinal Motility (Guangdong Provincial Standard, Appendix 2). Scores were documented daily from the day of surgery (before treatment) through postoperative Days 1–5, according to observed gastrointestinal function.
- **Quality of life assessment:** The Gastrointestinal Quality of Life Index (GIQLI) was employed (Appendix 3). Assessments were performed on the day of surgery prior to treatment, on postoperative Day 5, and again on Day 14 following the final treatment session.

5. Adverse Events and Management

If adverse reactions occurred during the trial—such as needle stagnation, syncope, breakage, hematoma, or infection—investigators promptly managed the event, ensured patient safety, reassured the participant with an explanation, and documented the details in the case report form.

6. Ethical Principle

This clinical trial was reviewed and approved by the Ethics Committee of Guangdong Provincial Hospital of Traditional Chinese Medicine prior to participant enrollment (Approval No. YF-2023-435-01). The study was conducted in full compliance with the principles of the Declaration of Helsinki.

7. Statistical Analysis

Data were organized and managed using Microsoft Excel to establish a primary database, which was subsequently converted into an SPSS 26.0 database for statistical analysis. The Shapiro–Wilk test was employed to assess the normality of continuous variables. According to data distribution, descriptive statistics were presented as mean \pm standard deviation (SD) for normally distributed variables, and as median with interquartile range [P₂₅, P₇₅] for non-normally distributed variables. Between-group comparisons of normally distributed data were performed using independent-samples t tests, while within-group pre- and post-treatment comparisons were conducted using paired t tests. For non-normally distributed data, the Mann–Whitney U test was applied for between-group comparisons, and the Wilcoxon signed-rank test for within-group comparisons.

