Categorical variables were expressed as frequencies (n) and percentages (%), with between-group comparisons analyzed using the chi-square test or Fisher's exact test, as appropriate. Repeated measures analysis of variance (ANOVA) was applied for comparisons across multiple time points between groups. All statistical analyses were two-tailed, and a P value of less than 0.05 was considered statistically significant.

8. References

2. Boeckxstaens GE, de Jonge WJ. Neuroimmune mechanisms in postoperative ileus. *Gut*. 2009;58(9):1300-1311. doi:10.1136/gut.2008.169250
4. Mythen MGM. Postoperative gastrointestinal tract dysfunction: an overview of causes and management strategies. *Cleve Clin J Med*. 2009;76 Suppl 4:S66-71. doi:10.3949/ccjm.76.s4.11
5. Kehlet H. Surgical Stress Response: Does Endoscopic Surgery Confer an Advantage? *World J Surg*. 1999;23(8):801-807. doi:10.1007/s002689900583

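### For the inflammatory markers two of the three measurements precede treatment, yet Section 7 analyses all three as outcomes in a repeated-measures ANOVA and does not say which term is the treatment effect

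*Protocol*

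**What the plan says.** Protocol 4.3.2 sets the schedule for the four inflammatory markers: "Each parameter was assessed once preoperatively, on the day of surgery prior to treatment, and on postoperative Day 5". Protocol 2.4.3.3 fixes the start of treatment: "The initial abdominal acupuncture treatment was performed 4–6 hours after surgery". The preoperative and day-of-surgery samples are therefore both untreated.

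Protocol Section 7 (Statistical Analysis) gives the rule for outcomes measured more than once: "Repeated measures analysis of variance (ANOVA) was applied for comparisons across multiple time points between groups". It lists no outcomes, but three-time-point markers fall under it. It does not say whether the group term or the group-by-time term answers the treatment question, and it gives the pre-treatment values no role as covariates. Section 7 also says "Between-group comparisons of normally distributed data were performed using independent-samples t tests", with Mann–Whitney U for non-normal data, and ties these tests to no time point.

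The quality-of-life index in 4.3.3 has the same feature to a lesser degree: "Assessments were performed on the day of surgery prior to treatment, on postoperative Day 5", and again 14 days after the last session. The symptom score has one pre-treatment and five later daily values.

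**The concern.** In a repeated-measures ANOVA the group main effect compares the arms on each patient's average over all time points. When randomisation makes the expected arm difference zero at two of three times, that average carries only a third of whatever happened at Day 5. An analyst who takes the sentence on comparisons between groups at face value could report this term, and so give too small an effect and probably a non-significant one. The interaction avoids the dilution but is not focused on the one contrast of interest. If the t test is also run, each marker has three candidate P values (group, interaction, Day 5) and no rule says which is the result.

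**Working it through.** **The plan's own figure.** The protocol states no effect, SD, correlation or power for the markers. Its only computed figure is the sample size for time to first flatus (2.4.4): "The required sample size was determined to be 33 participants per group". That figure does not follow from its inputs: 2 × (1.960 + 1.282)² × 4.11² / 8.1² = 5.4, so 6 per group. This is a separate matter. Here 33 per arm is used only as the planned number of analysable patients.

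**Inputs.**
- From the protocol: 33 per arm, two-sided alpha 0.05, two pre-treatment times and one post-treatment time.
- Assumed: effect D at Day 5 only; SD 1 at each time; common correlation ρ of 0.3, 0.5 or 0.7, with 0 and 0.9 as extremes; D = 0.6 SD, then 0.8 SD.

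**Group main effect.** Expected value: (0 + 0 + D)/3 = D/3. SD of a patient's three-time mean: √((1 + 2ρ)/3). For D = 0.6 the raw effect is 0.20. The SDs are 0.730, 0.816 and 0.894, so the standardised effects are 0.274, 0.245 and 0.224. Noncentral t, 64 df.

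**Day 5 t test.** Standardised effect 0.6, 64 df.

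**Group-by-time interaction.** Noncentrality = (33/2) × (2/3)D² / (1 − ρ) = 3.96/(1 − ρ), giving 5.66, 7.92 and 13.2. Noncentral F with 2 and 128 df.

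**Day 5 adjusted for the mean of the two pre-treatment values (ANCOVA).** Variance explained: R² = 2ρ²/(1 + ρ) = 0.138, 0.333, 0.576. Residual SD √(1 − R²) = 0.928, 0.816, 0.651. Noncentral t, 63 df.

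Power at D = 0.6 SD:

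| Comparison | ρ = 0.3 | ρ = 0.5 | ρ = 0.7 |
|---|---|---|---|
| Group main effect | 20% | 17% | 15% |
| Day 5 t test | 67% | 67% | 67% |
| Interaction, 2 df | 55% | 70% | 91% |
| Day 5 ANCOVA | 73% | 84% | 96% |

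At the extremes, ρ = 0 gives 28%, 67%, 40% and 67% in the same order. ρ = 0.9 gives 13%, 67%, over 99% and over 99%.

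At D = 0.8 SD and ρ = 0.3/0.5/0.7: group main effect 31/26/22%, Day 5 t test 89%, interaction 81/92/99%, ANCOVA 93/98/over 99%.

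**Sample-size equivalent.** For the group main effect to match the Day 5 t test, patient numbers must rise by a factor 9 × (1 + 2ρ)/3 = 3(1 + 2ρ). That is 4.8, 6.0 and 7.2 for ρ = 0.3, 0.5 and 0.7, and 3.0 to 8.4 for ρ from 0 to 0.9.

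**Other outcomes.** If the effect is constant at every post-treatment visit, the group main effect keeps 2/3 of it for the quality-of-life index (one of three times untreated) and 5/6 for the symptom score (one of six).

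**The case against.** The strongest reply is that Section 7 never makes the group main effect the treatment test. A repeated-measures ANOVA also yields the interaction, which keeps the Day 5 contrast, and the t test in the same section could be applied at Day 5. On this view all that is missing is a named term, which is normal SAP content. Much of that stands. A reader might infer that the trial will report marker effects at a third of their size. The documents do not support this as a fact, because it follows only if the group term is read.

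A reader might also infer that the interaction is an unsound test because the arms can differ in the change between the two untreated samples. That does not hold either. Under randomisation both expected pre-treatment differences are zero, so the interaction null is the same as no Day 5 effect, and a chance difference is ordinary type I error. Even the group term is zero when D is zero, so it is a valid test of the null. Its faults are low power and an estimate of D/3 in place of D.

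What the reply does not remove is the method that the protocol does state. It places untreated values among the outcomes when they would serve better as covariates. At every correlation checked, the adjusted Day 5 comparison has at least about the power of the group term, the interaction and the plain t test. That is a point about the choice made, not about detail left for later.

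**Conclusion.** The concern holds in a limited form. The schedule and the ANOVA rule do not fit together well. The pre-treatment values are treated as outcomes, the term carrying the treatment effect is not fixed, and one available reading (the group main effect) returns exactly D/3. The factor of one third needs only equal weighting of the three times and an effect confined to Day 5. The power figures (15–20% for the group term, 55–91% for the interaction, 73–96% for the adjusted comparison, all at 0.6 SD) also rest on assumed effect size, equal variances and a common correlation of 0.3–0.7, none of which the protocol gives.

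The reach is secondary. The markers are not the primary outcome. Time to first flatus is a single measurement per patient and is untouched, so nothing here weakens the primary comparison.

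**What to change.** In Section 7, for outcomes with pre-treatment measurements:

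1. Define the treatment effect as the between-arm difference at Day 5 (for the quality-of-life index, at each post-treatment visit) from a model with the pre-treatment value or values as covariates. Use ANCOVA, or a repeated-measures model of the post-treatment visits only.
2. Use a transformed scale if the marker is skewed, and report the difference with a 95% CI.
3. State that the ANOVA group main effect is not the treatment comparison.

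Covariate adjustment is preferable to a change score. Day 5 minus the mean of the two pre-treatment values has variance 1.5(1 − ρ), which exceeds 1 when ρ is below 1/3, so there it has less power than the unadjusted Day 5 t test (65% against 67% at 0.6 SD and ρ = 0.3).

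The cost is a few sentences. No visit, sample or patient is added, since every value needed is already collected.

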4.3.3 Relevant Assessment Scales

- **Pain assessment:** The Visual analogue scale (VAS) was applied (Appendix 1). Abdominal pain scores were recorded before and after treatment on the day of surgery (5 days after surgery).
- **Gastrointestinal symptom assessment:** Symptom scoring was based on the Perioperative Clinical Evaluation Standards for Gastrointestinal Motility (Guangdong Provincial Standard, Appendix 2). Scores were documented daily from the day of surgery (before treatment) through postoperative Days 1–5, according to observed gastrointestinal function.
- **Quality of life assessment:** The Gastrointestinal Quality of Life Index (GIQLI) was employed (Appendix 3). Assessments were performed on the day of surgery prior to treatment, on postoperative Day 5, and again on Day 14 following the final treatment session.

5. Adverse Events and Management

If adverse reactions occurred during the trial—such as needle stagnation, syncope, breakage, hematoma, or infection—investigators promptly managed the event, ensured patient safety, reassured the participant with an explanation, and documented the details in the case report form.

6. Ethical Principle

This clinical trial was reviewed and approved by the Ethics Committee of Guangdong Provincial Hospital of Traditional Chinese Medicine prior to participant enrollment (Approval No. YF-2023-435-01). The study was conducted in full compliance with the principles of the Declaration of Helsinki.

7. Statistical Analysis

Data were organized and managed using Microsoft Excel to establish a primary database, which was subsequently converted into an SPSS 26.0 database for statistical analysis. The Shapiro–Wilk test was employed to assess the normality of continuous variables. According to data distribution, descriptive statistics were presented as mean \pm standard deviation (SD) for normally distributed variables, and as median with interquartile range [P₂₅, P₇₅] for non-normally distributed variables. Between-group comparisons of normally distributed data were performed using independent-samples t tests, while within-group pre- and post-treatment comparisons were conducted using paired t tests. For non-normally distributed data, the Mann–Whitney U test was applied for between-group comparisons, and the Wilcoxon signed-rank test for within-group comparisons.

Categorical variables were expressed as frequencies (n) and percentages (%), with between-group comparisons analyzed using the chi-square test or Fisher's exact test, as appropriate. Repeated measures analysis of variance (ANOVA) was applied for comparisons across multiple time points between groups. All statistical analyses were two-tailed, and a P value of less than 0.05 was considered statistically significant.

8. References

2. Boeckxstaens GE, de Jonge WJ. Neuroimmune mechanisms in postoperative ileus. *Gut*. 2009;58(9):1300-1311. doi:10.1136/gut.2008.169250
4. Mythen MGM. Postoperative gastrointestinal tract dysfunction: an overview of causes and management strategies. *Cleve Clin J Med*. 2009;76 Suppl 4:S66-71. doi:10.3949/ccjm.76.s4.11
5. Kehlet H. Surgical Stress Response: Does Endoscopic Surgery Confer an Advantage? *World J Surg*. 1999;23(8):801-807. doi:10.1007/s002689900583

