2.4.5 Randomization

Randomization was performed using SPSS version 26.0. To ensure reproducibility of the randomization process, a Random Number Seed was first applied, followed by the generation of random numbers using the UNIFORM(Max) function. These random numbers were then used to assign participants into groups, and a randomization table was created accordingly. During clinical implementation, participants were allocated sequentially according to their order of enrollment by matching them to the corresponding numbers in the randomization table, and the designated treatment protocol was applied. In this study, the intervention group received abdominal acupuncture, while the control group received standard care.

3. Interventions

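### The VAS pain sentence assigns the scores both to the day of surgery and to five days after it, and no assessment time is fixed for the control arm

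*Protocol*

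**What the plan says.** The only statement of when pain is scored is in Protocol Section 4.3.3: "Abdominal pain scores were recorded before and after treatment on the day of surgery (5 days after surgery". Appendix 1, as supplied, carries only the name of the scale.

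Sections 2.4.3.3 and 3.2.5 set the acupuncture schedule: "The initial abdominal acupuncture treatment was performed 4–6 hours after surgery, followed by one session daily from postoperative day 1 through day 4". That makes five sessions, none of them on Day 5.

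The comparator appears in Section 2.4.5, "the intervention group received abdominal acupuncture, while the control group received standard care", and in Section 2.4.4, where controls are said to receive conventional therapy. Section 3.1 describes this as continuing postoperative management. No sham or control session is described.

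Section 7 plans unadjusted two-sample tests between groups, paired tests of pre- against post-treatment values within each group, and repeated measures ANOVA where there are several time points.

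**The concern.** Taken literally, one sentence puts the pain scores on Day 0 and also five days later. A change across a session on the day of surgery and a change over the whole course are different outcomes, and the protocol does not say which one the VAS is meant to capture.

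The anchor adds a second difficulty. Treatment is a dated event in the acupuncture arm but continuous care in the control arm. If the anchor is a session, treated patients have a post-session score for which controls have no stated equivalent. Those patients would also be rating their own pain after a needling and infrared-lamp session that they know they received.

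At stake are the meaning of the paired comparison, the time at which the arms are compared and the number of time points in any repeated-measures analysis. While the sentence stands, each of these could be settled after the data are seen.

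**Working it through.** No sample size, power or error-rate figure enters this point, and the plan gives no figure to reproduce. The check sets the sections side by side.

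**1. Timing of VAS against the other outcomes**

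| Outcome | Section | Timing |
|---|---|---|
| VAS | 4.3.3 | "Abdominal pain scores were recorded before and after treatment on the day of surgery (5 days after surgery" |
| Laboratory markers | 4.3.2 | "Each parameter was assessed once preoperatively, on the day of surgery prior to treatment, and on postoperative Day 5" |
| Symptom score | 4.3.3 | "Scores were documented daily from the day of surgery (before treatment) through postoperative Days 1–5" |
| GIQLI | 4.3.3 | "Assessments were performed on the day of surgery prior to treatment, on postoperative Day 5", and again at Day 14 after the last session |

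The other three have explicit days. VAS is the exception.

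**2. VAS against the session schedule.** Sessions fall on Day 0 and Days 1 to 4, so 1 + 4 = 5. There is no Day 5 session, so a Day 5 score cannot belong to a before-and-after pair around a session. It can only be a score after the course.

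**3. Schedules that the sentence allows**

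- **A, around the Day 0 session:** 2 scores, both on Day 0. Needles stay in for 30 minutes (Section 3.2.4), so the pair spans at least that long. The protocol does not say how soon after the session the second score is taken.
- **B, Day 0 before treatment and Day 5 after the course:** 2 scores. Counting Day 5 as 5 × 24 = 120 hours after surgery (an assumption) and the first session at 4–6 hours, the gap is 120 − 6 = 114 to 120 − 4 = 116 hours.
- **C, around every session:** 5 × 2 = 10 scores, the last pair on Day 4. A daily variant over Days 0 to 5 would give 6 scores.

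**4. What each means for controls**

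| Reading | Pre-treatment score in controls | Post-treatment score in controls |
|---|---|---|
| A | Clock time not stated | No defined counterpart |
| B | Clock time not stated | Day 5, same as the treated arm |
| C | Clock times not stated | No defined counterpart |

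The last column depends on the reading; the middle column does not. The middle gap is also not peculiar to VAS: laboratory markers, symptom score and GIQLI all use a Day 0 pre-treatment time without saying what it is for a patient who has no session.

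**5. Which analysis is informative.** Under B, the within-group change contains natural recovery as well as any treatment effect, so a paired test cannot separate the two. The Day 5 difference between arms can. Adjusting it for the Day 0 score is sound only if that score precedes treatment and is taken at a comparable postoperative time in both arms, which is why the unstated control-arm time matters.

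**The case against.** The strongest reply is that the sentence can be read coherently: the parenthesis explains when the post-treatment score is taken, giving Day 0 before treatment and Day 5 afterwards. The context favours this. Laboratory markers, GIQLI and the safety tests in Section 4.2 use those two occasions, the sessions end on Day 4, and Section 7 speaks of pre- and post-treatment values. This stands as the likeliest intent. It remains an inference, because the words attach both scores to the day of surgery and no other section corrects them.

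A reader might infer that the pre/post anchor cannot be applied to controls at all. The documents do not support that. Under reading B the Day 5 score applies equally to both arms, and a Day 0 score can be taken in controls once a matching time is named. The missing counterpart arises only under session-based readings.

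A reader might also infer that pain has largely resolved by Day 5, or that the tests must give different answers under each reading. The protocol contains no pain values, so neither can be shown.

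Finally, adjustment for baseline is often left to a SAP, and an unadjusted comparison of randomized groups is not invalid. That is fair. But Section 7 itself names the unadjusted and within-group tests, so the protocol has already stated a choice for VAS that can be improved.

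**Conclusion.** The concern holds in limited form. The VAS timing contradicts itself within one sentence of Section 4.3.3 and is not resolved elsewhere. Day 0 before treatment and Day 5 after the course is the probable meaning, on the assumption that VAS follows the same pattern as its neighbours. If the scores were in fact tied to sessions, the post-session score has no defined control-arm equivalent. On every reading, the control-arm clock time for the Day 0 pre-treatment score is missing, a gap common to several outcomes.

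The size is an unfixed schedule of 2 to 10 scores and a pre/post interval that may lie within Day 0 or span about 114 to 116 hours. No effect on the pain result can be quantified from the documents. VAS is one of several efficacy measures besides the primary outcome; time to first flatus and the sample size do not depend on it.

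**What to change.** 1. Reconcile the VAS sentence in Section 4.3.3 so that each score has one stated day and time relative to surgery, the same in both arms. On the likeliest reading these are a Day 0 score before any session, with a matched postoperative time for controls, and a Day 5 score. State the same control-arm Day 0 time for the laboratory, symptom-score and GIQLI assessments.
2. The protocol is written in the past tense with enrolment from December 2023 to December 2024. If the data are already collected, report the times recorded on the case report form for each arm instead of setting new ones.
3. In Section 7, base the VAS conclusion on the between-group comparison at Day 5, adjusted for the Day 0 pre-treatment score (for example by analysis of covariance), in place of the unadjusted test. Keep within-group paired tests out of the conclusion.
4. Report any score taken only around a session as descriptive for the treated arm, with no between-group test.

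The cost is a rewritten sentence in Section 4.3.3, a short addition for the other outcomes and a line in Section 7. No new measurement is needed if Day 0 and Day 5 scores were what the trial collected. If only session-based scores exist, a Day 5 comparison cannot be recovered afterwards, and the report should say so.

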2.4.3 Trial Flow

2.4.3.1 Screening Visit

Patients will be screened according to inclusion and exclusion criteria, eligible patients will be required to provide written informed consent and enter the baseline visit. Randomization will be performed before baseline assessment.

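### Section 7 compares the arms on secondary outcomes without adjusting for the pre-treatment values collected; the cost is precision only, and the clearest gain is for the laboratory markers

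*Protocol*

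**What the plan says.** Section 7 (Statistical Analysis) fixes the between-arm methods. For continuous data, "Between-group comparisons of normally distributed data were performed using independent-samples t tests"; the Mann-Whitney U test takes over when the data are not normal. For outcomes measured repeatedly, "Repeated measures analysis of variance (ANOVA) was applied for comparisons across multiple time points between groups". Paired t and Wilcoxon signed-rank tests are named for before-after changes within an arm. No between-arm analysis names a covariate.

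The pre-treatment values exist:

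- **CRP, IL-6, TNF-alpha, SII** (section 4.3.2): "Each parameter was assessed once preoperatively, on the day of surgery prior to treatment, and on postoperative Day 5".
- **GIQLI** (section 4.3.3): "Assessments were performed on the day of surgery prior to treatment", then at Day 5 and 14 days after the last session.
- **Symptom score** (section 4.3.3): "Scores were documented daily from the day of surgery (before treatment) through postoperative Days" 1 to 5.
- **VAS pain** (section 4.3.3): before and after treatment, although the sentence mentions both the day of surgery and five days later, so the post-treatment time is unclear.

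Three further statements matter. Section 2.4.4 sizes the trial on time to first flatus alone: "The required sample size was determined to be 33 participants per group". Section 2.4.3.1 says: "Randomization will be performed before baseline assessment". Section 2.4.5 says that "the intervention group received abdominal acupuncture, while the control group received standard care"; no sham procedure is described.

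**The concern.** A patient's marker level or symptom score before treatment usually predicts part of the later value. A t test or Mann-Whitney test on the later value leaves that predictable part in the error term. Repeated-measures ANOVA can take the pre-treatment value in, but as one more response and not as a covariate.

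The sample size was not chosen for these outcomes, so their precision depends on how they are analysed. They also bear on the stated aims: section 2.1 includes postoperative quality of life. If the collected baselines are informative, the planned comparisons give wider intervals and lower power than the same data allow.

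**Working it through.** **The plan's own figure.** The protocol states no power or precision for these outcomes, so there is nothing to reproduce for them. The only related figure is the 33 per group for time to first flatus. The stated formula and inputs (SD 4.11 h, difference 8.1 h, two-sided 0.05, 90% power) give 2 × (1.960 + 1.282)² × 4.11² / 8.1² = 5.41, or 6 per group, so 33 does not reproduce. That is a separate matter. Here 33 is used only as the stated number per arm.

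**Inputs.** n = 33 per arm (section 2.4.4); two-sided 0.05 (section 7); 80% power (my choice); correlation ρ between baseline and post-treatment value of 0.3, 0.5 or 0.7, with 0 as the limiting case. The protocol gives no ρ, so this is an assumed range.

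**Step 1: ANCOVA against the unadjusted post-treatment t test.** With post-treatment SD σ, the unadjusted difference has variance 2σ²/n. ANCOVA multiplies this by (1 − ρ²) and by a small-sample factor of about 1 + 1/(2n − 4) = 1 + 1/62 = 1.016.

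**Step 2: detectable difference.** By the normal approximation the unadjusted figure is (1.960 + 0.842) × √(2/33) = 0.69 SD. The noncentral t gives 0.700 SD on 64 degrees of freedom. ANCOVA uses 63 degrees of freedom and the reduced variance.

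| ρ | 1 − ρ² | × 1.016 | 33 per arm act like 33/(1 − ρ²) | Unadjusted, SD | ANCOVA, SD |
|---|---|---|---|---|---|
| 0 | 1.00 | 1.02 | 33 | 0.700 | about 0.71 (0.700 × √1.016) |
| 0.3 | 0.91 | 0.92 | 36 | 0.700 | 0.674 |
| 0.5 | 0.75 | 0.76 | 44 | 0.700 | 0.611 |
| 0.7 | 0.51 | 0.52 | 65 | 0.700 | 0.504 |

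A simulation of 20,000 trials with 33 per arm gave variance ratios of 1.02, 0.93, 0.77 and 0.51 at ρ = 0, 0.3, 0.5 and 0.7, in line with the formula.

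**Step 3: a single before-after change score.** With equal SDs before and after, a change score has variance 2(1 − ρ) relative to the post-treatment value. The ratio of ANCOVA to change score is (1 − ρ²) / [2(1 − ρ)] = (1 + ρ)/2 = 0.65, 0.75, 0.85. The change score detects 0.829, 0.700 and 0.542 SD. Against the better of the two unadjusted contrasts at each ρ, ANCOVA gains 0.700 − 0.674 = 0.026, 0.700 − 0.611 = 0.089 and 0.542 − 0.504 = 0.038 SD.

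**Step 4: where Step 3 applies.** It describes one baseline and one follow-up. The markers and GIQLI have three time points, and the symptom score has six (day of surgery and Days 1 to 5). With three or more levels the arm-by-time test has several degrees of freedom and is not a simple change score. Step 3 is therefore not the gain over the planned ANOVA, and neither Step 1 nor Step 3 describes Mann-Whitney.

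**Step 5: the symptom score.** Taking the timed rows in Appendix 2 as readings behind the temperature item, its maximum is 15 + 15 + 7 × 10 = 100. Flatus and defecation supply 30 of these points and are probably absent in most patients before the first session. That part of the baseline would hardly vary, so little gain is expected.

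**The case against.** The strongest reply is that nothing here is wrong. Unadjusted tests are valid under randomisation, the protocol promises no precision for these outcomes, and a separate analysis plan might add adjustment. The first two parts stand. The third carries less weight, because section 7 names the between-arm tests itself, so this is a stated choice rather than an open detail.

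The gain is also modest and rests on an assumed ρ. That stands: against the better unadjusted contrast it is 0.03 to 0.09 SD. The equal-SD assumption matters less than it may seem. It is needed for the change-score ratios but not for 1 − ρ², which depends only on the correlation and a roughly linear relation.

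A reader might infer that 0.65, 0.75 and 0.85 measure the gain over the planned repeated-measures ANOVA. The schedules in sections 4.3.2 and 4.3.3 do not support that, as Step 4 shows.

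A reader might also infer that every outcome should simply be switched to an adjusted analysis. The design argues against it. Baseline follows randomisation and the control is standard care, so self-reported baselines may be given with the allocation known. Adjusting for a covariate affected in that way can bias the estimate, while a post-treatment comparison does not use it. Reporting both shows the risk but does not remove it. Laboratory values, above all preoperative ones, are much less exposed.

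Finally, it may be too late. Section 2.4.2.1 gives enrolment as December 2023 to December 2024, and the reference list carries an access date in September 2025. This limits what can still be called prespecified.

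**Conclusion.** The point holds as a matter of precision. Section 7 does not use collected baselines as covariates when it compares the arms. For an assumed ρ of 0.3, 0.5 or 0.7, ANCOVA would have about 0.91, 0.75 or 0.51 of the variance of the unadjusted post-treatment t test, with a cost of about 2% if ρ is zero. The gain over the multi-time-point ANOVA and over Mann-Whitney is not quantified.

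A reader might infer bias, an inflated false-positive rate or a threat to the main result. None follows: the stated tests are valid, and time to first flatus has no baseline to adjust for. The case is firmest for the laboratory markers, weaker for the patient-reported scales, and slight for the symptom score. It ranks between optional and a low-priority recommendation.

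**What to change.** - **Laboratory markers:** estimate the between-arm difference at Day 5 by ANCOVA with arm and the preoperative value, both marker values on the log scale, and report it with a confidence interval.
- **GIQLI, symptom score and VAS:** give the baseline-adjusted estimate beside the unadjusted one and call it supportive, stating that baseline followed randomisation without a sham control. For VAS, first state the post-treatment time clearly.
- **If the data have already been analysed:** keep the section 7 tests as the planned analysis and label all adjusted results supplementary and post hoc.

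The cost is slightly more modelling. No new data, visit or procedure is needed.
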